## **5.5 RECRUITMENT PROCEDURES**

Participants will be identified for potential recruitment using pre-screening enrollment logs, clinical database, referrals from other clinicians, patient groups, and Institutional Review Board (IRB)/Independent Ethics Committees (IEC) approved participant-facing recruitment materials prior to consenting to take place in this study.

## **6. TREATMENTS**

Study treatment is defined as any investigational product (including placebo) or marketed product intended to be administered to a study participant according to the study protocol.

The investigational medicinal products (IMP) for this study are basmisanil and placebo. *Appendix 6* identifies all IMPs and auxiliary medicinal products (AxMPs)/non-investigational medicinal products (NIMPs). All IMPs required for completion of this study will be provided by the Sponsor.

Cases of overdose, medication error, drug abuse, or drug misuse, along with any associated AEs, should be reported as described in [Appendix 2](#), Section 5.2.

### **6.1 TREATMENTS ADMINISTERED**

*Table 8* and *Table 9* summarize the treatments administered in Part 1 and Part 2, respectively. Guidelines for dosage modification and treatment interruption or discontinuation are provided in Section 6.6 or Section 7, respectively.

**Table 8 Summary of Treatments Administered in Part 1**

Study Treatment Name:	Basmisanil (RO5186582)	Placebo
Doseb:		
Route of Administration:	oral	oral
Sourcing:	Provided centrally by the Sponsor	
Packaging and Labeling:	Study treatment will be provided in boxes. Each box will be labeled as required per country requirement.	

BID = twice a day; NA = not applicable; TID = three times a day.

a Study treatment will be provided [REDACTED]

[REDACTED] The number of stick-packs to be taken per administration will depend on the participant's age at the time of signing the Informed Consent Form.

b Doses are determined according to the age of the participant at the time of signing the Informed Consent Form and will not change if a participant moves into another age group.

These are the starting doses for participants being enrolled in Part 1, [REDACTED] (see Sections 4.1 and 6.6).

**Table 9 Summary of Treatments Administered in Part 2**

Study Treatment Name:	Basmisanil (RO5186582)
Use:	
Dose Formulation:	
Unit Dose Strength:	
Doseb:	
Route of Administration:	oral
Sourcing:	Provided centrally by the Sponsor
Packaging and Labeling:	Study treatment will be provided in boxes. Each box will be labeled as required per country requirement.

*BID = twice a day; PBPK = physiologically-based pharmacokinetic; PK = pharmacokinetic; TID = three times a day.*

a *Study treatment will be provided [REDACTED]. No placebo is used in Part 2. The number of stick-packs to be taken per administration will depend on the participant's actual age.*

b *These are the starting doses for participants in Part 2. The starting dose will be determined according to the actual age of the participant at the start of Part 2 (Day 366 visit) and the dose must be changed at the latest on the first dispensation visit after the participant moved into a different age group (see Section 4.1).*

*Dose and dose regimen for participants aged 15 to 17 years are predicted to be similar to what has been determined as the starting steady state regimen in Part 1 for 10 to 14 years old [REDACTED]*

*Dose or dose regimen may be adapted during the study (see Sections 4.1 and 6.6).*

Please see Section 6.4 for details on the requirements for study treatment administration as well as the [Basmisanil Investigator's Brochure](#) for more details.

## 6.2 PREPARATION/HANDLING/STORAGE/ACCOUNTABILITY

Study treatment packaging will be overseen by the Sponsor's clinical study supplies department and will bear a label with the identification required by local law, the protocol number, drug identification, and dosage.

The packaging and labeling of the study treatment will be in accordance with the Sponsor's standard and local regulations.

The study site should follow all instructions included with each shipment of IMP. The investigational site will acknowledge receipt of IMPs and confirm the shipment condition and content. Any damaged shipments will be replaced. The investigator or designee must confirm that appropriate temperature conditions have been maintained during transit for all IMPs received, and that any discrepancies have been reported and resolved before use of the IMPs. All IMPs must be stored in a secure, environmentally controlled, and monitored (manual or automated) area in accordance with the labeled storage conditions with access limited to the investigator and authorized staff.

Only participants enrolled in the study may receive IMPs, and only authorized staff may supply or administer IMPs. Study treatment will be dispensed at the study visits or shipped to the participant's home (where local regulations allow for home shipments). Caregivers will be instructed on IMP administration, storage and return. Returned study treatment should not be re-dispensed to the participants.

The study site (i.e., Investigator or other authorized personnel [e.g., pharmacist]) is responsible for maintaining records of IMP delivery to the site, IMP inventory at the site, IMP use by each participant, and disposition or return of unused IMP, thus enabling reconciliation of all IMP received, and for ensuring that participants are provided with doses specified by the protocol. The study site may also be responsible for shipping IMP to the participant's home. Upon arrival of the IMPs at the site, site personnel will complete the following:

- Check the IMPs for damage.
- Verify proper identity, quantity, integrity of seals and temperature conditions.
- Report any deviations or product complaints to the Study Monitor upon discovery.

The Investigator or delegate must confirm appropriate temperature conditions have been maintained during transit for all study treatment received and any discrepancies are reported and resolved before use of the study treatment.

All study treatments must be stored in a secure, environmentally controlled, and monitored (manual or automated) area in accordance with the labeled storage conditions with access limited to the Investigator and authorized site staff.

The Investigator is responsible for study treatment accountability, reconciliation, and record maintenance (i.e., receipt, reconciliation, and final disposition records). *Unused IMP stick-packs will have to be returned by the caregiver at clinic visit or via the shipping courier to the study site for drug accountability and reconciliation.*

IMPs will either be disposed of at the study site according to the study site's institutional standard operating procedure or returned to the Sponsor with the appropriate documentation. The site's method of IMP destruction must be agreed upon by the Sponsor. Local or institutional regulations may require immediate destruction of used

IMP for safety reasons. The site must obtain written authorization from the Sponsor before any IMP is destroyed, and IMP destruction must be documented on the appropriate form. Accurate records of all IMPs received at, dispensed from, returned to, and disposed of by the study site should be recorded on the drug accountability log.

Refer to the [Basmisanil Investigator's Brochure](#) for information on IMP formulation, IMP handling, including preparation and storage, and accountability.

## **6.3 MEASURES TO MINIMIZE BIAS: RANDOMIZATION AND BLINDING**

### **6.3.1 Method of Treatment Assignment**

All participants will be centrally randomized to study treatment using an Interactive Voice/Web Response System (IxRS). Before the study is initiated, the telephone number and call-in directions for the IVRS and/or the login information and directions for the IxRS will be provided to each site.

Randomization will be stratified by

- Age group (2 to 5 years vs. 6 to 14 years)
- Number of copies of the 15q11.2-q13.1 region (3 copies vs. 4 copies)
- Epilepsy (presence vs. absence)

*In Part 2 all participants are assigned to receive open-label basmisanil, regardless of their treatment assignment in Part 1.*

### **6.3.2 Blinding**

*Part 1 is a double-blind study, i.e., the study participants, the Investigators, all individuals in direct contact with the study participants at the investigative site, and the Sponsor Study Management Team (SMT) will be blinded to treatment assignment. PK data can be transferred and cleaned on an ongoing basis. The data will be handled and cleaned in a secure area that is not accessible by any blinded SMT member.*

Members of the IMC and SOC will review unblinded aggregated information. Selected IMC and SOC members may be unblinded also at a participant level (see Section [4.1.2.1](#)). Individual study team members outside the IMC and SOC required to prepare information for IMC and SOC review will be unblinded to the treatment assignment at the participant level. Access to treatment assignment information will follow the Sponsor's standard procedures.

### **Emergency Unblinding**

If unblinding is necessary for participant management in the case of an SAE, the Investigator will be able to break the treatment code by contacting the IxRS. Treatment codes should not be broken except in emergency situations. If the Investigator wishes to

know the identity of the study treatment for any other reason, he/she should contact the Medical Monitor directly. The Investigator should document and provide an explanation for any premature unblinding (e.g., accidental unblinding, unblinding due to an SAE).

As per Health Authority reporting requirements, the Sponsor will break the treatment code for all unexpected SAEs (see Section 8.3.3.1) that are considered by the Investigator to be related to study treatment. The participant may continue to receive treatment, and the Investigator, participant, and Sponsor personnel, with the exception of the Drug Safety representative and personnel who must have access to participant treatment assignments to fulfill their roles (as defined above), will remain blinded to treatment assignment.

Whenever disclosure of the identity of the test medication is necessary, adequate procedures will be in place to ensure integrity of the data.

#### **6.4 TREATMENT COMPLIANCE**

The qualified individual responsible for dispensing the study treatment will write the date dispensed and participant number on the study treatment label and on the Drug Accountability Record. This individual will also record the study treatment number received by each participant during the study.

The study treatment granules are packaged in stick-packs, which have to be cut open with scissors and not ripped.

*On the first day of treatment in Part 1 (Day 1), the study treatment is taken BID, in the morning and in the evening, at the clinical study site. Thereafter, the study treatment is taken TID, at least 3 hours apart and within 30 minutes after the start of a meal.*

*Caregivers will use a drug diary to record missed study treatment administration throughout the study (see Section 8.1.3.1). If a dose is missed (i.e., there would be less than 3 hours until the next dose), it must not be taken with the next dose and recorded as missed dose in the drug diary. The following dose should be taken at the usual time.*

#### **6.5 CONCOMITANT THERAPY**

Concomitant therapy includes any medication, e.g., prescription drugs, over-the-counter (OTC) drugs, vaccines (including COVID-19 vaccines), approved dietary and herbal supplements and nutritional supplements used by a participant from 6 weeks prior to

screening until the follow-up visit. *See also stability requirements for a ketogenic diet in Section 5.3.*

**Anti-epileptic medication** must be on a stable regimen 8 weeks prior to screening and for at least the first 4 weeks of treatment *in Part 1*. After the Day 28 visit, dose adjustments within the therapeutic range, and changes within the same class of anti-epileptic medication may be allowed as part of routine clinical care, upon consultation with the Medical Monitor. *In Part 2, for the first 28 days (until Day 395) dose changes are not allowed. Changes in the number or the class of anti-epileptic medications are not allowed until the Part 1 follow-up visit for participants who do not continue study participation in the optional OLE or until the Day 548 visit for participants who roll over to Part 2 of the study.*

The Medical Monitor should be contacted if there are any questions regarding concomitant or prior therapy.

All concomitant medications should be reported to the Investigator and recorded on the Concomitant Medications electronic Case Report Form (eCRF) along with reason for use, dates of administration (including start and end dates) and dosage information (including dose and frequency).

All medication administered to manage AEs should be recorded on the Adverse Event eCRF.

**Non-pharmacological** (e.g., physiotherapy) / **behavioral therapies** should not be stopped or newly started at least 6 weeks prior to screening and are expected to remain stable *until the Part 1 follow-up visit or until the Day 548 visit for Part 2 participants (excluding changes related to standard age and educational interventional programs or minor interruptions such as illness or vacation).*

Non-pharmacological / behavioral therapies should be reported on the *appropriate* eCRF page.

### **6.5.1      Permitted Therapy**

Permitted therapy includes all medication used by a participant to manage symptoms associated with Dup15q syndrome *that is not specified as prohibited therapy in Section 6.5.2, taken from 6 weeks prior to screening until the Part 1 follow-up visit or until the Day 548 visit for participants in Part 2.*

Participants who use oral contraceptives with a failure rate of <1% per year; see Section 5.1 and [Appendix 5](#), hormone-replacement therapy, or other maintenance therapy should continue their use.

## **6.5.2        Prohibited Therapy**

The below listed therapies are prohibited and should not be administered within 2 weeks (or within 5-times the elimination half-life, whichever is longer) prior to dosing and until the Follow-up visit, unless otherwise specified. Methods of administration, which do not produce appreciable systemic drug exposure (e.g., topical administration for skin conditions), are permitted:

### **Modulators of CYP3A4 Activity**

Basmisanil is predominantly cleared by metabolism via CYP3A4, and concomitant medications that significantly alter CYP3A4 activity will affect the pharmacokinetics of basmisanil.

Strong inhibitors of CYP3A4 (e.g., itraconazole, erythromycin, fluconazole, nefazodone, ritonavir, verapamil, grapefruit or grapefruit juice) taken within 2 weeks (or within 5-times the elimination half-life, whichever is longer) prior to dosing is prohibited. Moderate CYP3A4 inhibitors may be used after discussion with the Medical Monitor and eventual use of inhibitors of CYP3A should be accompanied by dedicated safety monitoring, in particular the QT.

Inducers of CYP3A4 (e.g., rifampicin, carbamazepine, pioglitazone, rifampin, modafinil, systemic glucocorticoids, oxycarbazepine, carbamazepine, phenobarbital, phenytoin, St John's Wort) taken within 4 weeks prior to dosing (or within 5 × times the elimination half-life, whichever is longer) are not permitted.

### **Dofetilide**

Dofetilide use is not permitted because of the potential for interaction between basmisanil and renally cleared cationic drugs, as well as the very narrow therapeutic window of dofetilide.

### **Benzodiazepines (chronic use)**

Based on the potential for interactions to occur between basmisanil and other medications whose effects are mediated via GABAA receptors, chronic use of benzodiazepines, including as treatment for epilepsy (e.g., clobazam) is not allowed.

Restrictions for acute use of benzodiazepines are described in Section 6.5.3.

## OTC Cannabidiol (CBD)

Use of artisanal CBDs (products, derivatives, cannabis plants/extracts) is prohibited. Epidiolex/Epidyolex is not prohibited.

### 6.5.3 Therapy to be Used with Caution

[REDACTED]

[REDACTED]

#### Concomitant medications with an effect on QT

Drugs known to prolong the QTc interval will be allowed if stable at screening provided the screening QTc does not meet exclusion QTc criterion. Use of currently approved prokinetics (e.g. domperidone, metoclopramide) is not prohibited, but requires closer monitoring of QTc interval on ECG due to risk of arrhythmias.

#### Benzodiazepines / GABAergic medications

Benzodiazepines and benzodiazepine-related drugs may be exceptionally used with the following restrictions:

- **For the treatment of intermittent medical conditions** (e.g., for insomnia and anxiety / agitation, analgosedation)
  - Medications with a short half-life (e.g., lorazepam, alprazolam, or oxazepam) are preferred
  - Short-term use only (no more than 4 days per month)
  - Should not be taken within 2 days before a scheduled visit
- **For the treatment of emergency situations** (e.g., for the acute management of a seizure)
  - *If benzodiazepines/benzodiazepine-related drugs are required in an emergency situation, the visit can be rescheduled to allow for a 2-day window between emergency medication and visit date (even if it falls out of the protocol defined visit window).*
  - If benzodiazepines, in particular diazepam, midazolam, or clonazepam are used, the Investigator should be aware that a higher-than-normal dose of the medication may be required to achieve clinical response.
  - Similarly, in case of acute use of anesthetics that are GABAA positive allosteric modulators (e.g., volatile anesthetics or hypnotics) in a participant treated with

basmisanil, a higher dose of the anesthetics may be required to achieve the desired effect.

As described above, these recommendations are based on the potential for competition (PD interaction) at the GABAA receptor level.

## **6.6 DOSE MODIFICATION, TEMPORARY INTERRUPTION AND RECHALLENGE**

[REDACTED]

[REDACTED]

[REDACTED]

[REDACTED]

[REDACTED]

[REDACTED]

### **6.6.1 Temporary Interruption**

Before permanently discontinuing study treatment (regardless of whether initiated by the participant/*caregiver*, the Investigator or Sponsor), an interruption should be considered. Temporary study treatment interruption is an acceptable method to manage AEs related to the study treatment.

Participants who have temporarily interrupted should be considered for restarting study treatment as soon as medically justified in the opinion of the Investigator.

Study treatment should be interrupted if individual stopping rules are met (see Section 4.1.3) and to manage specific AEs and resumed as detailed in Section 8.3.8. Study treatment may be resumed with the joint agreement of the Investigator and the Sponsor's Medical Monitor when follow-up test results show that the participant no longer meets the dose interruption criteria. Unless it is determined by the Investigator that the occurrence is not related to the administration of the study treatment, study treatment should not be restarted.

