#### **4.1.3 Stopping Rules Criteria**

Dosing will be stopped at any time during the study in a given individual participant if one of the following circumstances occurs:

- A QTc using the Fridericia's correction factor (QTcF) value > 480 msec (when confirmed in repeat measurement within 30 minutes) or a QTcF change from baseline > 60 msec (when confirmed in repeat measurement within 30 minutes) for participants **older than 10 years old**;

OR

- A QTc using Bazett's formula (QTcB) value > 480 msec (when confirmed in repeat measurement within 30 minutes) or a QTcB change from baseline > 60 msec (when confirmed in repeat measurement within 30 minutes) for participants **up to, and including, the age of 10 years** (Bazett's correction is more appropriate in young children, see Section 8.2.6).
- Worsening of seizure frequency or occurrence of de novo seizures, which are considered clinically relevant in the opinion of the Investigator based on the following criteria:
  - persistent over time,
  - OR
  - notably deviate from the expected fluctuations in seizure status based on the participant's medical history,
  - OR
  - cannot be explained by the expected natural course of the disease,
  - OR
  - making the benefit-risk ratio non-favorable for the individual.

Other AEs that may lead to discontinuation of study treatment following evaluation on a case-by-case basis are described in Section 8.3.8. Before permanently discontinuing study treatment, an interruption should be considered, and study treatment may be restarted as detailed in Section 6.6.1. Unless it is determined by the Investigator that the occurrence is not related to the administration of study treatment, study treatment should not be restarted (see Section 7.1).

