## **6.7 TREATMENT AFTER THE END OF PART 1 OF THE STUDY**

All participants who complete the 52 weeks of study treatment *in Part 1* will be offered the option to roll over into an *OLE* to receive basmisanol treatment for a duration of

approximately 2 years (Part 2). Participants will be required to sign a separate ICF for participation in Part 2.

A participant will not be eligible to receive study treatment after the end of *Part 1* of the study if any of the following conditions are met:

- The study treatment is commercially marketed in the participant's country and is reasonably accessible to the participant (e.g., is covered by the participant's insurance or would not otherwise create a financial hardship for the participant).
- The Sponsor has discontinued development of the study treatment or data suggest that the study treatment is not effective for Dup15q syndrome.
- The Sponsor has reasonable safety concerns with regards to the study treatment.
- Provision of study treatment is not permitted under the laws and regulations of the participant's country.
- The participant discontinued prematurely from study treatment or withdrew from the study before completing 52 weeks of treatment.

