**Table 12 Guidelines for Managing Specific Adverse Events (cont.)**

Elevated liver enzymes	

• ALT or AST <math>> 3 \times</math> ULN:

◦ Monitor weekly until ALT and AST return to <math>\leq 1.2 \times</math> ULN.

◦ Further investigation into the liver enzyme elevations may include hepatitis serologies and other diagnostic tests at the discretion of the investigator in consultation with the Medical Monitor.

• Interrupt the study treatment in the event of liver enzymes that meet the following criteria:

◦ ALT or AST <math>> 5 \times</math> ULN

◦ ALT or AST <math>> 3 \times</math> ULN and either total bilirubin <math>> 2 \times</math> ULN or INR <math>> 1.5</math>

◦ ALT or AST <math>> 3 \times</math> ULN associated with symptoms (new or worsening) believed to be related to liver injury or hypersensitivity

◦ Such abnormalities should be followed by repeat testing within 48 to 72 hours and repeated two to three times weekly based on the participant's clinical state. An evaluation by a hepatologist may be required if the abnormalities do not stabilize. All participants with possible drug-induced liver injury should be followed until abnormalities return to normal, even if the study treatment has been discontinued.

◦ Discontinue study medication permanently if levels do not return to baseline after 30 days

------------------------	---

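### Section 6.6.1 both allows and forbids restarting treatment after a related adverse event that has resolved, so the same event can count as an interruption or as a premature discontinuation

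*Combined protocol and SAP*

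**What the plan says.** Section 6.6.1 has three short paragraphs.

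- The first asks that interruption be considered before permanent discontinuation and adds: "Temporary study treatment interruption is an acceptable method to manage AEs related to the study treatment".
- The second reads: "Participants who have temporarily interrupted should be considered for restarting study treatment as soon as medically justified in the opinion of the Investigator".
- The third applies interruption to events meeting the individual stopping rules and to specific AEs, with resumption as set out in Section 8.3.8. It lets treatment resume if the Investigator and the Medical Monitor agree, "when follow-up test results show that the participant no longer meets the dose interruption criteria". Its last sentence allows restart only where the Investigator determines that the event is unrelated; otherwise the rule is no restart: "the occurrence is not related to the administration of the study treatment, study treatment should not be restarted".

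Section 4.1.3 opens with "Dosing will be stopped at any time during the study in a given individual participant" for the listed QTc and seizure events. Its closing paragraph refers to other AEs that may lead to discontinuation, asks for interruption to be considered first, points to Section 6.6.1 for restart, and then repeats the causality bar with a reference to Section 7.1.

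The one row of Table 12 that can be read, on liver enzymes, says: "Discontinue study medication permanently if levels do not return to baseline after 30 days". It does not mention causality.

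Section 6.7 lists, among the conditions that end eligibility for treatment after Part 1: "The participant discontinued prematurely from study treatment or withdrew from the study before completing 52 weeks of treatment".

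**The concern.** Interruption is offered expressly for AEs related to treatment, yet the last sentence of the same section removes restart for exactly that class. An interruption that can never end in restart is a discontinuation under another name.

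The classification has consequences in the trial:

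- The incidence of treatment discontinuations due to AEs is a secondary safety endpoint of Part 1 (Table 5). Its value would depend partly on how Section 6.6.1 was read.
- Under Section 7.1 a participant who discontinues treatment prematurely is asked to attend an early termination visit and then follow-up. Table 1 includes a Vineland-3 at early termination, but not at the scheduled Week 52 timepoint that the primary comparison uses (Section 9.1).
- Under Section 6.7 that participant can no longer receive treatment in Part 2.

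**Working it through.** No arithmetic applies, and the plan gives no figure to reproduce. The check is whether the restart statements can all hold for the same event.

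**Statements compared**

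- A (6.6.1, first paragraph): interruption may be used for related AEs.
- B (6.6.1, second paragraph): consider restart when the Investigator finds it medically justified. No causality condition.
- C (6.6.1, third paragraph): resume by agreement with the Medical Monitor when the interruption criteria are no longer met. No causality condition.
- D (6.6.1, last sentence): no restart unless the event is determined to be unrelated.
- E (4.1.3, closing paragraph): consider interruption and restart as in 6.6.1, then the same bar as D.

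**Applied to three cases**

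| Event | B and C | D | Result |
|---|---|---|---|
| Unrelated, resolved | restart possible | no bar | consistent |
| Related, criteria still met | C not satisfied | barred | consistent: no restart |
| Related, resolved | restart possible | barred | contradiction |

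The conflict is confined to the third case, which falls in the class that A names. E does not settle it, because E contains both halves.

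**Can the scope be narrowed?** One could read D as covering only stopping-rule events. But the paragraph holding D covers stopping rules and specific AEs together, and nothing limits which occurrence is meant. In Section 4.1.3 the same sentence comes after the reference to other AEs.

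**Can the conditions be cumulative?** Recovery, agreement and unrelatedness could all be required. That makes the third paragraph coherent on its own. Interruption for a related AE could then never end in restart, so A and B would have no effect for related events.

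**Table 12.** The liver row makes discontinuation permanent when values have not returned to baseline after 30 days. It does not say what happens to a related elevation that recovers sooner, or whether D also applies. The row leaves the question open.

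**Other signs of intent.** The title of Section 6.6 includes rechallenge, and Appendix 2, Section 3.2 tells investigators to weigh the effect of reintroducing treatment when judging causality. Both suppose that restart after a possibly related event can happen. Neither says when.

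**The case against.** The strongest reply is that the governing text may be out of sight. The body of Section 6.6 is redacted, Section 6.6.1 sends specific AEs to Section 8.3.8, and only one row of Table 12 can be read. A clarifying rule may exist there. This stands as a limit on the finding. It does not remove the conflict, because the contradictory sentences sit together in visible text and neither is made subject to another rule that would reconcile them.

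It can also be said that restart under the third paragraph needs the Medical Monitor's agreement, which is a central check. That stands too: it should reduce differences between sites, though it does not tell the Medical Monitor which sentence governs.

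A reader might infer more than the documents support:

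- **That Sections 4.1.3 and 6.6.1 conflict because one says stopped and the other interrupted.** The closing paragraph of 4.1.3 itself provides for interruption and restart through 6.6.1, so this difference in wording is not a conflict.
- **That Table 12 promises restart on recovery.** It states only when discontinuation becomes permanent. A separate causality condition could stand beside it.
- **That the losses fall mainly on basmisanil.** Investigators judge causality blinded (Section 6.3.2), and the bar applies by default unless unrelatedness is determined, so placebo participants can be caught as well.
- **That the loss can be counted.** With 2:1 randomization of about 90, the basmisanil arm is about 90 × 2/3 = 60. An assumed 5% to 10% rate of related interruptions would give 3 to 6 participants, but nothing in the documents supports that rate. Setting it against the roughly 9 (10% of 90) assumed non-evaluable would compare one arm with both, and those 9 may already include such cases.
- **That these participants drop out of the primary analysis.** They remain in the intent-to-treat set (Table 13), early termination includes a Vineland-3, and the text of the primary analysis is redacted.

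**Conclusion.** Wrong as written. For an AE judged related that has resolved, Section 6.6.1 both permits and forbids restart, and Section 4.1.3 repeats the pair. For unrelated events, and for related events that still meet the interruption criteria, the statements agree.

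The effect is on classification. The reading chosen moves a participant between interruption and premature discontinuation, with consequences for one secondary safety endpoint, the timing of the last Vineland-3, and entry to Part 2. The documents allow no estimate of how many participants this touches or whether the arms differ.

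The conclusion rests on the visible wording and assumes that the redacted body of Section 6.6 and the unseen rows of Table 12 do not already limit the bar. Even if they do, the last sentence of Section 6.6.1 needs a cross-reference to that limit.

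**What to change.** First check the redacted Section 6.6 and the full Table 12 for an existing rule. Then reconcile Section 6.6.1 with the closing paragraph of Section 4.1.3, and align Section 7.1 and Table 12, so that:

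- the scope of the causality bar is stated once, saying which events it covers among stopping-rule events, listed specific AEs and other related AEs;
- each of those event types has one consistent statement on interruption, restart and permanent discontinuation;
- Table 12 says whether the bar applies in addition to its recovery condition.

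The clinical rule is for the sponsor to decide; this point asks only that the passages agree. The cost is protocol wording at the next amendment.
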